### 7.3.2 Inclusion criteria

The patient is 18-90 years old The patient suffers from a GI stricture The stricture is amenable for endoscopic dilation The patient has undergone at least 1 previous endoscopic dilation for the same stricture within the last 3 months The patient has signed the ICF

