# Part I : Trial related part of the protocol

# 1 Title of the trial

Local injection of collagenase clostridium histolyticum (XiapexR) for refractory gastrointestinal strictures: an open-label pilot study.

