# 3 Objective of the study

To investigate whether intralaesional injection with collagenase clostridium histolyticum (XiapexR) into the stricture followed by dilation 24 hours later improves the outcome of patients with refractory gastrointestinal strictures as compared to dilation alone (standard of care).

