# 4 End point(s) and timepoint(s) of evaluation

### Primary outcome measure:

Number of repeat dilations that are required over a timespan of 6 months.

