### Secondary outcome measures:

1) time to first repeat dilation

- 2) complication rate.
- 3) For upper gastrointestinal strictures only: Dysphagia/gastric outlet obstruction

score (0:, able to eat normal diet; 1: moderate passage: able to eat some solid foods;

2: poor passage: able to eat semi-solid foods only; 3: very poor passage: able to drink liquids only; 4: no oral intake possible

4) For lower gastrointestinal strictures only: (Ileo)colorectal obstruction scoring system (0, requiring continuous decompression; 1, no oral intake; 2, liquid or enteral nutrition; 3, oral intake of soft solids, low-residue diet, or full diet with symptoms of stricture\*; and 4, oral intake of soft solids, low-residue diet, or full diet without symptoms of stricture\*. Symptoms of stricture include abdominal pain/cramps, abdominal distension, nausea, vomiting, constipation, and diarrhea which are related to gastrointestinal transit).

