# 6 Introduction

The main causes of benign gastrointestinal (GI) strictures are inflammatory (eg: reflux disease, eosinophilic esophagitis, Crohn's disease, caustic...) or iatrogenic (postirradiation, post endoscopic (sub)mucosal resection, post radiofrequency ablation, anastomotic...). Most strictures respond well to endoscopic balloon dilation. Nonetheless, more than one third of patients develop recurrent symptoms after dilation within the first year (1).

In some case, the stricture can be difficult to treat and require multiple dilation sessions to obtain long-term relief of dysphagia, eating difficulties or lower GI obstructive symptoms (2, 3). A refractory stricture is defined as a cicatricial or fibrotic narrowing luminal diameter resulting in clinical symptoms of a) dysphagia (esophageal strictures), b) gastric outlet obstruction (for strictures of the stomach, pylorus, duodenum of gastrojejunal anastomosis) or c) lower GI obstruction (abdominal distension and cramps, vomiting) with an inability to successfully remediate the anatomic problem to a sufficient diameter over 3 dilation sessions at two-week intervals (4). A recurrent stricture is defined as a cicatricial or fibrotic narrowing with an inability to maintain a satisfactory luminal diameter for four weeks (4). Several options (stenting, intralesional injection of corticosteroids, needle knife incision) have been proposed to manage these strictures, with a varying success rate (5). A significant proportion of patients will finally need self-bougienage or surgery (5).

In conclusion, the treatment of GI strictures remains a challenge for clinicians and there is an unmet need for novel approaches to manage the patients suffering from this condition in order to avoid repeated dilations and/or invasive surgery.

XiapexR is a locally injectable collagenase approved for the management of Dupuytren's and Peyronie's disease (6, 7). Xiapex is a mixture of two collagenases, enzymes produced by the bacterium *Clostridium histolyticum* that dismantle collagen. Approximately 24 hours after local injection, the collagen fibres have lost their

strength and can be easily broken by manipulation. This therapy has been a breakthrough in the management of Dupuytren's disease, avoiding surgery in the vast majority of patients (6).

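### The listed entry criteria are not linked to the protocol's own definition of a refractory stricture, and the historical controls have no such link, calendar window or index dilation, so the comparison can reflect entry severity or time zero rather than the drug

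*Combined protocol and SAP*

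**What the plan says.** The title describes injection "for refractory gastrointestinal strictures: an open-label pilot study". The objective asks whether the treatment "improves the outcome of patients with refractory gastrointestinal strictures as compared to dilation alone (standard of care"). Sections 7.3.1 (both groups) and 8.1 (those who receive the injection) use the same word, refractory.

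Section 6 gives the meaning: symptomatic fibrotic narrowing with "inability to successfully remediate the anatomic problem to a sufficient diameter over 3 dilation sessions at two-week intervals". It defines a second category separately: "A recurrent stricture is defined as a cicatricial or fibrotic narrowing with an inability to maintain a satisfactory luminal diameter for four weeks".

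The inclusion list in 7.3.2 covers age, a GI stricture, suitability for dilation, consent, and one item on prior treatment: "The patient has undergone at least 1 previous endoscopic dilation for the same stricture within the last 3 months". It does not mention refractory status or section 6. The only exclusion (7.3.3) concerns language.

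The controls (7.3.1) are 40 consecutive patients at the centre, dilated to 12-15 mm for a refractory stricture. Their outcomes come from file review (8.1). The primary outcome is "Number of repeat dilations that are required over a timespan of 6 months", and the first secondary outcome is "time to first repeat dilation". Section 12.3 plans a descriptive comparison with this cohort.

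**The concern.** The threshold in the inclusion list is lower than the one in the definition: one dilation in three months against failure over three sessions. If sites screen by the list, the active group may not be the population in the objective.

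The control side is open in a different way. The label is there, but the protocol does not say how it is established from old files, from which date the 40 are counted, or which of a patient's several dilations starts the 6 months. The three-month rule for active patients is not stated for controls.

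The outcome depends on this. Section 6 says "Most strictures respond well to endoscopic balloon dilation", and contrasts these with strictures that need many sessions. With no randomisation, and no matching or adjustment stated, comparable entry and a comparable time zero are the main protection that the comparison could have. What is at stake is the decision whether to take the treatment further, because no formal test is planned.

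**Working it through.** **1. Do the criteria and the definition differ in practice?** Take a patient dilated once 11 weeks ago, whose narrowing recurred after 6 weeks and who is now due a second dilation in any case (7.3.6 says that the study adds none).

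| Test | Requirement | This patient |
|---|---|---|
| 7.3.2, prior dilation | at least 1 in 3 months (about 91 days) | 1, at 77 days: met |
| Section 6, refractory | failure over 3 sessions | 1 session: not met |
| Section 6, recurrent | diameter not held for four weeks | held 6 weeks: not met |

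Such a patient can satisfy every clinical item in 7.3.2 and neither definition in section 6.

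**2. How far could a difference in mix move the comparison?** The plan has no figure to reproduce: section 12.1 gives no sample size calculation, and no rates of repeat dilation appear anywhere. Everything below except the group sizes 10 and 40 is therefore an assumption. Let mr and mn be the mean repeat dilations in 6 months for refractory and non-refractory patients, and pa and pc the non-refractory shares of the active and control groups. With no drug effect,

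ratio = [(1 - pa) mr + pa mn] / [(1 - pc) mr + pc mn].

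With mr = 4 and mn = 1.5 (range over mr 3 to 6 and mn 1 to 2 in the last column):

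| Non-refractory patients | Calculation | Ratio | Range |
|---|---|---|---|
| 3 of 10 active, 0 of 40 controls | (0.7 x 4 + 0.3 x 1.5) / 4 = 3.25 / 4 | 0.81 | 0.75-0.90 |
| 0 of 10 active, 12 of 40 controls | 4 / 3.25 | 1.23 | 1.11-1.33 |
| same share in both | equal numerator and denominator | 1.00 | 1.00 |

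The shift can go either way, and it vanishes when the mix is the same.

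**3. Would the outcome data show it?** Take the same mix in both groups, no drug effect, mean 4, and individual rates that vary as a gamma distribution with shape 4. The variance of a count is 4 + 4²/4 = 8. The standard error of the log ratio is about √[8/(16 x 10) + 8/(16 x 40)] = √(0.05 + 0.0125) = 0.25, which gives exp(±1.96 x 0.25) = 0.61 to 1.63. Simulation of 10 against 40 patients gives a central 95% range of about 0.58 to 1.57. Both 0.81 and 1.23 lie well inside it.

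**4. Does the choice of index dilation matter?** The same gamma assumption (mean 4 per 182 days) was used to simulate patients over a one-year window. The mean count in the next 182 days is 4.04 from the first dilation in the window and 3.69 from a randomly chosen one. From the last it is 3.11, but that is low by construction. This shows that the rule can matter, not how much it would matter here.

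**The case against.** The strongest reply is that the protocol, read as a whole, already restricts entry. Section 6 defines refractory, 7.3.1 applies the word to both groups, and 8.1 makes it a description of those who are injected. That stands as far as it goes. A reader might infer that the protocol has no definition of refractory, or that non-refractory patients will be enrolled. The documents support neither. What is missing is the link: no listed criterion tests the status, and the one on prior dilation sets a different threshold.

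Second, this is a small descriptive pilot, and historical controls are never fully comparable. That limits the consequence, and no test or error rate is affected. But the objective and 12.3 still compare the groups, and these particular gaps can be closed by wording.

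Third, the illustrated shifts are smaller than chance variation with 10 and 40 patients. True, but chance does not cancel a systematic difference. It means that the outcome data could not expose one.

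Two further readings go too far. One is that every secondary outcome is affected: the argument applies to time to first repeat dilation, but nothing in the documents ties, for example, complication rate to refractory status. The other is that baseline comparison has been ruled out: 12.3 is silent on it.

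**Conclusion.** The concern holds as a missing link and a conflicting threshold in the active group, together with a control cohort that lacks a link to the definition, a calendar window and an index dilation. The comparison of repeat dilations, and of time to first repeat dilation, can therefore reflect different entry severity or a different time zero rather than the drug.

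A reader might infer a bias in favour of the drug. The documents do not support a direction: milder active patients would lower the ratio, loosely labelled controls would raise it, and equal mixes would leave it alone. The ratios of 0.81 and 1.23 rest wholly on assumed means and mixes, and are not estimates for this trial. This should be fixed; the pilot remains feasible.

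**What to change.** Reconcile 7.3.2 with section 6 and 7.3.1, and apply one written entry rule to both groups.

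- **Population.** Either 7.3.2 and the control selection both refer to the section 6 definition, or the controls are selected by the clinical items of 7.3.2 and the title and objective describe that population. The sponsor decides which. If the definition is used, the sponsor also needs to state how a sufficient diameter is judged, both prospectively and from files, because section 6 gives it no value. The consent item cannot be a control criterion as it stands, since 8.1 seeks consent only from controls still followed at the department.
- **Control window and index.** Before control outcomes are reviewed, fix a calendar window that closes at least 6 months before file review, and one index rule. An example is the first 12-15 mm dilation in the window at which the patient meets the entry rule; other rules are acceptable if fixed in advance. Take the 40 consecutive patients in order of that date.
- **Time zero.** Count the 6 months from the index dilation in controls and from the Day +1 dilation in active patients.
- **Baseline table.** Show the number and timing of prior dilations, stricture site and cause for both groups. Site and cause belong there because they could differ even under one entry rule.

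The cost is wording in 7.3.1 and 7.3.2 (and in the title and objective under the second option), a short chart-review rule and some extra file review. Recruitment of the 10 patients may be slower if the section 6 definition is adopted.

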### 7.3.3 Exclusion criteria

The patient is not fluent in Dutch

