After local injection, the collagenases do not reach the bloodstream in significant amounts and are presumed to largely stay at the point of injection until they are broken down by proteases. As a result, side effects are uncommon and are most often injection site reactions including lymphadenopathy (swollen lymph nodes), itching, pain, oedema, and bleeding (for example in the form of bruises or ecchymoses). Allergic reactions are seen in less than 1% of patients (8).

XiapexR has been proposed as a promising treatment for refractory urethral strictures but has never been evaluated in refractory GI strictures (9).

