## 7.2.8 Known side effects of the medication

After local injection the collagenases do not reach the bloodstream in significant amounts and are presumed to largely stay at the point of injection until they are broken down by proteases. As a result, side effects are uncommon and are most often injection site reactions including lymphadenopathy (swollen lymph nodes), itching, pain, oedema, and bleeding (for example in the form of bruises or ecchymoses). Allergic reactions are seen in less than 1% of patients Drug accountability

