### 7.3.6 Possible advantages and risks for the subjects

It is possible that participation to the study will result in less need for repeat dilations for a refractory upper GI stricture (unknown).

Every dilation carries the risk of perforation, even in the most experiences hands. No additional dilations are performed in light of the study. It is unknown whether local injection of the study drug augments the risks of perforation. Every patient is carefully monitored after dilation (standard of care). Upon clinical suspicion of perforation, a CT scan is performed for confirmation.

suspicion of perforation, a CT scan is performed for confirmation. In case of confirmed perforation, endoscopic stenting is immediately performed to bridge the defect, allowing healing of the defect. The stent can most of the time be removed after 6 weeks. In some case, endoscopic clipping is the treatment of choice to close the iatrogenic perforation. Surgical intervention is seldomly needed

Side effects of the study drug (XiapexR) are expected to be very limited, as the study drug does not enter the bloodstream in significant amounts and is rapidly degraded in the bloodstream by proteases. Local reactions (bleeding, swelling, inflammation) are theoretically possible. Like all foreign substances, Xiapex can induce allergic reactions but these seem to be very rare (only 1 case described in literature).

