# 10 Prior and concomitant therapy

Patients on anticoagulant medication need to interrupt the treatment according to the recommendations of the treating physician ([name] or [name]).

All other prior or concomitant medications are allowed

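### The protocol's only exclusion criterion is language, so the written eligibility rule admits a patient known to have reacted allergically to the study collagenase (minor safety point).

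*Combined protocol and SAP*

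**What the plan says.** The exclusion list in protocol section 7.3.3 has a single entry: "The patient is not fluent in Dutch".

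The inclusion criteria in section 7.3.2 cover age, the presence of a GI stricture, its suitability for dilation, signed consent, and this item on treatment history: "The patient has undergone at least 1 previous endoscopic dilation for the same stricture within the last 3 months". None concerns allergy.

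On other medicines, section 10 asks only for anticoagulants to be interrupted as the treating physician advises, and then states: "All other prior or concomitant medications are allowed".

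On the hazard, section 7.2.8 says: "Allergic reactions are seen in less than 1% of patients". Section 6 has the same sentence. Section 7.3.6 accepts that the product can cause allergic reactions but calls them very rare, citing one published case.

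On earlier exposure, section 6 describes the product as "approved for the management of Dupuytren's and Peyronie's disease".

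**The concern.** An exclusion list is where a protocol normally keeps a study drug away from patients already known to be harmed by it. Here the protocol recognises allergic reaction as a risk and notes that the product is approved for two other conditions. A candidate could therefore have been treated with it before and have reacted. Nothing in the eligibility text keeps that patient out.

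What is at stake is the safety of an individual patient. The protocol plans only descriptive analyses (12.3), and this point does not bear on them. A known reactor has little to lose by exclusion, because section 7.3.4 gives non-participants endoscopic dilation as usual care.

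**Working it through.** The main check is a reading of the text; the arithmetic only bounds the size. The plan gives no figure for known reactors, so there is none to reproduce.

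**Step 1: is there a bar or a screening step anywhere?**

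| Protocol section | Content relevant here | Stops a known reactor? |
|---|---|---|
| 7.3.2 Inclusion criteria | Age, stricture, suitability for dilation, earlier dilation, consent | No |
| 7.3.3 Exclusion criteria | Language only | No |
| 7.3.4 Replacement of subjects | Standard care for non-participants; single dose | No |
| 7.3.5 Restrictions | Fasting, anticoagulants | No |
| 7.3.6 Advantages and risks | Names allergy as a risk; sets no eligibility rule | No |
| 8.1 and 8.2 Procedures, flowchart | Consent between day -7 and day -1, then injection on day 0; no allergy question listed | No |
| 10 Prior and concomitant therapy | Anticoagulant interruption; other medicines permitted | No |

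Section 10 is a rule on permitted medicines. It shows that earlier collagenase treatment is no obstacle to entry, but it does not address a previous reaction.

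**Step 2: is there an indirect safeguard?**

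- Section 7.2.6 (Labelling) keeps the commercial label in use and unobscured.
- Section 11, under the definition of an unexpected adverse event, gives the package insert or summary of product characteristics as the example of reference information for an approved product.
- Section 11 also mentions a medical history section of the CRF, in connection with events between consent and first dose.

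None of these is an eligibility criterion. What the label says about patients who have reacted, and what the CRF asks, cannot be read from the documents.

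**Step 3: how many patients could it affect?**

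Inputs:

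- n = 10 treated patients (section 7.3.1).
- r < 0.01, the allergic reaction rate (sections 6 and 7.2.8).
- e, the share of candidates treated with the product before. The documents do not give it, so the full range 0 to 1 is shown.

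Assuming that r applies to candidates who were exposed before:

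expected known reactors = n × r × e < 10 × 0.01 × e = 0.1 × e

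| e | Expected known reactors among 10 |
|---|---|
| 0 | 0 |
| 0.1 | below 0.01 |
| 0.5 | below 0.05 |
| 1 | below 0.1 |

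The row e = 1 is a limit, not an estimate: it would require every candidate to have been treated for another condition with this product. The single published case cited in section 7.3.6 points lower still.

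**The case against.** The strongest reply is that the harm is almost hypothetical. It needs a patient with a GI stricture who was treated with this product for another disease, reacted, still consents, and meets a physician who injects regardless. Nothing in the documents suggests that such patients are common, and the product's commercial label travels with each vial. On this view the missing line is standard wording and nothing more.

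Most of that stands: the case is very rare and a physician would probably decline. What remains is that the written rule, followed exactly, admits the patient, and that a physician can act only on a history that has been taken. The protocol does not require anyone to ask.

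Several stronger readings are tempting, and the documents do not support them:

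- *That nothing at all protects the patient.* The label and the product information are in play, although their content is not available here.
- *That allergy history is not collected.* The CRF and the consent form were not available. Only the protocol's silence can be shown, which is no basis for demanding a new CRF entry.
- *That the three mentions of allergy are three pieces of evidence.* Sections 6 and 7.2.8 repeat one sentence; section 7.3.6 adds that reactions are very rare.
- *That the novelty of the GI use makes the danger greater for a known reactor.* Section 6 does say that the product has not been evaluated in refractory GI strictures. A known reactor's risk, however, comes from that patient's own history and would arise in the approved uses too.
- *That pregnancy should be excluded on the same argument.* The protocol does not name pregnancy as a risk of this drug. Section 11 makes it reportable, and the unknown effect on perforation (7.3.6) applies to every participant.

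**Conclusion.** The point holds as a minor patient-safety improvement, and not as a material defect of the design. No protocol section bars or screens for a known previous allergic reaction to the study product, although the protocol itself names that risk.

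The size is an expected number below 0.1 × e among 10 patients, hence below 0.1 in the most extreme case. This assumes that the protocol's figure of under 1% applies to previously exposed candidates; e is unknown. No point estimate is possible. The case for acting rests on a foreseeable hazard and a very cheap remedy, not on frequency.

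The conclusion concerns the protocol text only. It would lose most of its force if the CRF or the consent procedure already asks about earlier reactions and acts on the answer.

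**What to change.** Add one exclusion to section 7.3.3: *known hypersensitivity or previous allergic reaction to collagenase clostridium histolyticum*. State in section 8.1 or 8.2 that this is asked by history at the existing consent contact (day -7 to day -1), before the day 0 injection.

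The cost is a short amendment and one question at a contact that already takes place, with no added visit, test or procedure. The downside is that a rare patient becomes ineligible and receives standard dilation (7.3.4), which might slow recruitment of the 10 patients slightly.
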